3.1.2. Exclusion Criteria

1. Male patients
2. Patients with endometrioid, clear cell, mucinous, or sarcomatous histology, mixed tumors containing any of the above histologies, or low-grade/borderline ovarian tumor
3. Patients with primary platinum-refractory disease, defined as disease that did not respond to (CR or PR) or has progressed within 3 months of the last dose of first-line platinum-containing chemotherapy
4. Patients with prior wide-field radiotherapy (RT) affecting at least 20% of the bone marrow
5. Patients with $>$ Grade 1 peripheral neuropathy per Common Terminology Criteria for Adverse Events (CTCAE)
6. Patients with active or chronic corneal disorders, history of corneal transplantation, or active ocular conditions requiring ongoing treatment/monitoring, such as uncontrolled glaucoma, wet age-related macular degeneration requiring intravitreal injections, active diabetic retinopathy with macular edema, macular degeneration, presence of papilledema, and /or monocular vision
7. Patients with serious concurrent illness or clinically relevant active infection, including, but not limited to the following:
 - a. Active hepatitis B or C infection (whether or not on active antiviral therapy)
 - b. Human immunodeficiency virus (HIV) infection

- c. Active cytomegalovirus infection
- d. Any other concurrent infectious disease requiring IV antibiotics within 2 weeks prior to the first dose of MIRV

Note: Testing at screening is not required for the above infections unless clinically indicated

- 8. Patients with a history of multiple sclerosis (MS) or other demyelinating disease and/or Lambert-Eaton syndrome (paraneoplastic syndrome)
- 9. Patients with clinically significant cardiac disease including, but not limited to, any of the following:
 - a. Myocardial infarction \leq 6 months prior to first dose
 - b. Unstable angina pectoris
 - c. Uncontrolled congestive heart failure (New York Heart Association $>$ class II)
 - d. Uncontrolled \geq Grade 3 hypertension (per CTCAE)
 - e. Uncontrolled cardiac arrhythmias
- 10. Patients with a history of hemorrhagic or ischemic stroke within 6 months prior to enrollment
- 11. Patients with a history of cirrhotic liver disease (Child-Pugh Class B or C)
- 12. Patients with a previous clinical diagnosis of noninfectious interstitial lung disease (ILD), including noninfectious pneumonitis
- 13. Patients requiring use of folate-containing supplements (eg, folate deficiency)
- 14. Patients with prior hypersensitivity to monoclonal antibodies (mAb)
- 15. Women who are pregnant or breastfeeding
- 16. Patients who received prior treatment with MIRV or other FR α -targeting agents
- 17. Patients with untreated or symptomatic central nervous system (CNS) metastases
- 18. Patients with a history of other malignancy within 3 years prior to enrollment
Note: patients with tumors with a negligible risk for metastasis or death (eg, adequately controlled basal-cell carcinoma or squamous-cell carcinoma of the skin, or carcinoma in situ of the cervix or breast) are eligible
- 19. Prior known hypersensitivity reactions to study drugs and/or any of their excipients

Prospective approval of protocol deviations to recruitment and enrollment criteria, also known as protocol waivers or exemptions, is not permitted.

4. INVESTIGATIONAL PLAN

4.1. Study Design

4.1.1. Overview and Schema

This Phase 3 study is designed to evaluate the efficacy and safety of MIRV in patients with platinum-resistant high-grade serous EOC, primary peritoneal, or fallopian tube cancer, whose

tumors express a high level of FR α . Patients will be, in the opinion of the Investigator, appropriate for single-agent- therapy. FR α expression will be defined by the Ventana FOLRI Assay.

Approximately 110 patients who have provided informed consent and meet study entry criteria will be enrolled to achieve a total of 105 efficacy evaluable patients. Efficacy evaluable patients include those who have measurable lesions (per RECIST v1.1) at baseline and received at least 1 dose of MIRV.

Enrolled patients will receive single-agent MIRV at 6 mg/kg AIBW administered Q3W.

Tumor response will be evaluated by the Investigator using RECIST v1.1. CT or MRI scans will be collected for sensitivity analysis by a BICR.

Patients will continue to receive MIRV until PD, unacceptable toxicity, withdrawal of consent, death, or until the Sponsor terminates the study (whichever comes first).

Tumor assessments, including radiological assessment by CT/MRI scan, will be performed at Screening and subsequently every 6 weeks (\pm 1 week) from C1D1 for the first 36 weeks then every 12 weeks (\pm 3 weeks) until PD, death, the start of new anticancer therapy, or patient's withdrawal of consent, whichever occurs first.

Patients who discontinue MIRV for reasons other than progressive disease (PD) will continue with tumor assessments until documentation of PD or the start of a new anticancer therapy, whichever comes first. Prior to Week 36 (from Cycle 1, Day 1), assessments should occur every 6 weeks (\pm 1 week) as allowed by local requirements but must occur at an interval of no more than 12 weeks. After Week 36, assessment will occur every 12 weeks (\pm 3 weeks) until documentation of PD or the start of new anticancer therapy.

All patients who discontinue study drug will be followed every 3 months (\pm 1 month) until death, lost to follow-up, withdrawal of consent for survival follow-up, or EOS, whichever comes first.

There will be no interim analysis.

4.1.2. Dose and Schedule for Mirvetuximab Soravtansine

MIRV will be administered at 6 mg/kg on Day 1 of every 3-week cycle (Q3W).

5. STUDY TREATMENT

5.1. Mirvetuximab Soravtansine

The investigational study drug, MIRV, will be provided by ImmunoGen, at a protein concentration of 5.0 mg/mL in an aqueous pH 5.0 buffered solution. See the [Investigator Brochure](#) for complete list of excipients.

5.1.1. Mirvetuximab Soravtansine Packaging

MIRV will be provided in a 20 mL glass, single-use Type I vial. The container closure for the Type I glass vials will consist of a 20 mm ETFE-coated serum stopper (Flurotec[®]) with a 20 mm aluminum TruEdge[®] seal with blue Flip-off[®] top.

Refer to the Pharmacy Manual for labeling information.

5.1.2. Mirvetuximab Soravtansine Accountability

Specific details regarding storage and handling of MIRV can be found in the Pharmacy Manual.

Accountability and shipping documents for MIRV must be maintained by the Principal Investigator (PI) or designee (eg, the study pharmacist). The Investigator or designee must maintain an accurate record of all MIRV received, stored, dispensed, destroyed, and used in an Investigational Product Dispensing/Accountability Log or equivalent. These records must always be available for inspection, and a copy will be supplied to ImmunoGen on request. Information recorded on the Accountability Log will include dates and quantities of drug received, dates and quantities of drug dispensed, patient number and initials to whom drug is administered, lot number of drug administered, the recorder's initials, and dates and quantities of drug destroyed or returned. Upon receipt, vials should be visually inspected for vial integrity (ie, cracks or leaks) and a record of any damaged or suspect drug should be kept on the Accountability Log.

Upon completion of the study, all MIRV dispatched to a site must be accounted for and unused supplies destroyed according to the site's Standard Operating Procedures (SOPs) or returned to depot (refer to Pharmacy Manual). The original drug reconciliation records shall be maintained at the site and a copy collected and sent to ImmunoGen or designee once a representative of the company has confirmed the drug accountability.

Drug accountability will be monitored.

5.1.3. Mirvetuximab Soravtansine Study Treatment Compliance

MIRV supplied for the study may not be used for any purpose other than the study or administered other than as described in this protocol.

If necessary, MIRV from different drug lots may be mixed in a single-dose administration.

Under no circumstances is the Investigator allowed to release study drug supplies to any physician not named in the Food and Drug Administration (FDA) Form 1572 (or equivalent) to administer these supplies to a patient not enrolled in this study. If investigational supplies are to be dispensed from any facility other than that supervised directly by the PI (ie, hospital pharmacy, satellite pharmacy), it is the responsibility of the PI to ensure that all study drug is stored and administered as described (refer to Pharmacy Manual for instructions).

5.2. Assignment of Patient Number

Patient numbers are assigned in sequential order as patients sign the pre-screening informed consent to participate.

5.2.1. Enrolled Patient Definition

Patients who have consented to the study and have received at least 1 dose of study treatment, are considered enrolled. Patients who are issued a patient number, but who do not successfully complete the screening process and are not treated will be considered screen failures. Patient numbers for patients who screen fail will not be re-issued.

5.2.2. Patient Assignment to Dosing Regimens

All patients will receive MIRV 6 mg/kg AIBW Q3W.

5.3. Blinding Methods

Not applicable as this is an open-label, single-arm study.

5.4. Study Treatment Administration

5.4.1. Premedication for Study Treatment

All patients must receive 325 to 650 mg of acetaminophen/paracetamol (PO or IV), 10 mg IV dexamethasone, and 25 to 50 mg diphenhydramine (IV or PO) (equivalent drugs of similar drug classes is also acceptable) approximately 30 min before each infusion of MIRV. If individual patients require more intensive treatment to prevent infusion-related reactions (IRRs), investigators may modify the regimen accordingly. An antiemetic medication (eg, 5-HT₃ serotonin receptor antagonists such as palonosetron, granisetron or ondansetron or appropriate alternatives) is recommended before each MIRV dose and may be used any time at the discretion of the treating physician.

5.4.2. Prophylactic use of Eye Drops

5.4.2.1. Corticosteroid Eye Drops

All patients will be mandated to use corticosteroid eye drops as prescribed by the treating physician unless the risk outweighs the benefit as per the ophthalmologist/physician. All patients will be instructed to self-administer 1% prednisolone (Pred Forte[®] or generic equivalent) 6 times daily on Days -1 to 4 and QID on Days 5 to 8 of each cycle during the study. For individual patients who cannot tolerate the preservative contained in 1% prednisolone, other corticosteroid eye drops may be substituted (eg, difluprednate 0.05%; Durezol[®]) and administered on Days -1 to 8 of each cycle at a frequency prescribed by the ophthalmologist.

5.4.2.2. Lubricating Artificial Tears

Patients will be mandated to use preservative-free, lubricating artificial tears on a daily basis (as directed by the product label or the treating physician). Patients should be advised to wait at least 15 minutes after corticosteroid eye drop administration before instilling lubricating eye drops.

5.4.3. Preparation and Administration of Mirvetuximab Soravtansine

5.4.3.1. Calculation for Adjusted Ideal Body Weight

The total dose of MIRV is calculated based on each patient's AIBW using the following formula:

Adjusted Ideal Body Weight (AIBW)

$$\text{AIBW} = \text{IBW}^1 + 0.4 (\text{Actual weight} - \text{IBW}^1)$$

Where:

Ideal Body Weight (IBW)

$$\text{IBW}^1 (\text{female}) = 0.9\text{H}^1 - 92$$

¹H=height in cm; W=weight in kg)

The weight used for calculation should be obtained before study drug administration on C1D1 (-14 days) and thereafter should only be modified for significant ($\geq 10\%$) changes in body weight (not influenced by weight gain or loss attributed to fluid retention).

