Grade 2: Moderate	
 • Interrupt infusion and disconnect infusion tubing from patient • Promethazine (or equivalent) 150 mg PO per day (Q4h) PRN for nausea • Diphenhydramine (or equivalent) 25-50 mg PO or IV PRN • Acetaminophen (or equivalent) 650 mg PO PRN • Methylprednisolone (or equivalent) 125 mg IV PRN • After recovery from symptoms, resume the infusion at 50% of the previous rate and if no further symptoms appear, gradually increase rate until infusion is completed. • For subsequent dosing in future cycles, patients should be pre-medicated with Dex (or equivalent) 8 mg PO BID the day before drug administration and acetaminophen (or equivalent) 650 mg PO and diphenhydramine (or equivalent) 25-50 mg PO 30-60 min before dosing.
Grade 3: Severe, prolonged reaction not rapidly responsive to symptomatic medication and/or brief interruption of infusion; recurrence of symptoms after initial improvement; hospitalization indicated for clinical sequelae OR Grade 4: Life-threatening consequences, urgent intervention indicated	
 • Immediately stop infusion and disconnect infusion tubing from patient. • Administer diphenhydramine (25-50 mg) IV (or equivalent) • Administer IV steroids (methylprednisolone (or equivalent) up to 0.5mg/kg Q 6h) to treat ongoing reaction and prevent recurrence • Administer bronchodilators (nebulized albuterol/salbutamol, 2.5-5 mg in 3 mL of saline or equivalent) as medically indicated • Administer normal saline as medically indicated • Administer epinephrine (0.2-0.5 mL of a 1:1000 dilution (0.2-0.5 mg) SQ or IM) as medically indicated. Epinephrine should only be used if all other treatment methods fail to manage the IRR. • Advise patient to seek emergency treatment and notify Investigator/clinic if the infusion-related symptoms recur after discharge from clinic. • Report as an SAE (see Section 8.1.1.2). • Permanently discontinue study medication treatment

Abbreviations: BID = twice a day; CTCAE = common terminology criteria for adverse events; Dex = dexamethasone; IM = intramuscular; IRR = infusion-related reaction; IV = intravenously; PO = orally; PRN = as needed; SAE = serious adverse event; SQ = subcutaneous.

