6.1. Exposure

Summary tables will be provided with the following information.

Exposure to MIRV will be summarized with descriptive statistics for the number of doses received, the number of cycles received, duration of dosing (weeks), total cumulative dose (mg), absolute dose intensity (mg/kg/dose, calculated as total cumulative dose [mg])/number of valid drug administration records /AIBW [kg]).

The number of infusions with dose decreased, and dose delayed will also be summarized.

A listing will be provided with the information from all MIRV administration case report forms (CRFs) over the treatment period.

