- An overall summary of safety will summarize the numbers of patients with TEAEs of each grade and the number of patients who died during the study or within 30 days of last dose.
- All TEAEs.
- Serious TEAEs.
- Non-Serious TEAEs (ie, TEAEs excluding SAEs).
- Grade 3 or higher TEAEs.
- TEAEs leading to drug withdrawal. This subset includes TEAEs with an action taken of drug permanently discontinued.
- Related TEAEs leading to drug withdrawal. This subset includes TEAEs related to MIRV with an action taken of drug permanently discontinued.
- TEAEs related to MIRV.
- Serious, related TEAEs.
- TEAEs leading to dose modifications (dose reduction or dose delay).
 - TEAEs leading to dose reduction.
 - TEAEs leading to dose delay.
 - TEAEs leading to dose reduction or dose delay.
- Related TEAEs leading to dose modification (dose reduction or dose delay).
 - Related TEAEs leading to dose reduction.
 - Related TEAEs leading to dose delay.
 - Related TEAEs leading to dose reduction or dose delay.
- Deaths on study treatment or within 30 days of the last dose. This table includes all deaths during study treatment or within 30 days of the last dose, regardless of cause of death.
- TEAEs leading to death. This table includes all TEAEs with CTCAE Grade 5.
- Related TEAEs leading to death. This table includes all TEAEs related to MIRV with CTCAE Grade 5.

The following listings will be produced:

- All pre-treatment AEs will be listed.
- All AEs, sorted chronologically by patient. This listing includes SOC, PT, onset and end dates, and other relevant information.

- Serious TEAEs, sorted chronologically within patient.
- TEAEs leading to drug withdrawal. This subset includes TEAEs with an action taken of drug permanently discontinued.
- TEAEs leading to dose reduction or dose delay.
- TEAEs related to MIRV.
- Serious TEAEs related to MIRV.
- TEAEs resulting in death. This listing includes TEAEs with a CTCAE grade of Grade 5 (death).
- All deaths, with an indication of whether the death occurred on study or within 30 days of the last dose.

The following groupings of TEAEs will be generated as part of the focused analysis of safety:

- Ocular TEAEs.
 - A list of PTs for ocular AEs will be provided and finalized by the Sponsor before the final database lock.
- Peripheral neuropathy TEAEs.
 - A list of PTs for peripheral neuropathy AEs will be provided and finalized by the Sponsor before the final database lock.
- Pneumonitis.

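### The SAP's mg/kg-per-dose summary divides by a single AIBW, although the protocol resets the dosing weight after a 10% change, so the figure is off for re-weighed patients

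*Protocol*

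**What the plan says.** Protocol section 5.2.2 sets the regimen: "All patients will receive MIRV 6 mg/kg AIBW Q3W". Section 5.4.3.1 defines AIBW as ideal body weight (IBW) plus 0.4 times the difference between actual weight and IBW, where IBW for a woman is 0.9 times height in cm, minus 92. The same section fixes the weight and says when it may change: "The weight used for calculation should be obtained before study drug administration on C1D1 (-14 days) and thereafter should only be modified for significant" changes in body weight, set at 10% or more and excluding those attributed to fluid. After such a change AIBW is recalculated, and the mg given at the same mg/kg level changes with it.

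SAP section 6.1 lists absolute dose intensity, in mg/kg/dose, among the exposure statistics: "calculated as total cumulative dose [mg])/number of valid drug administration records /AIBW [kg". The AIBW carries no date, and no rule covers a patient whose dosing weight changed. Elsewhere the SAP refers to AIBW as a baseline characteristic (section 4.1.2).

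Dose changes are counted separately. SAP 6.1 adds: "The number of infusions with dose decreased, and dose delayed will also be summarized". SAP 6.2 tabulates "TEAEs leading to dose modifications (dose reduction or dose delay").

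**The concern.** The numerator adds up mg that may have been calculated on two or more body weights, while the denominator uses one. When the AIBW is constant the formula is exact. When it is not, a change in body weight shows up as a change in dose per kg, although the dose level in mg/kg was the same throughout. If the one AIBW is the baseline value, a patient who lost weight reads below her true mg/kg and a patient who gained weight reads above it. If it is the last value, the directions reverse. Anyone using this statistic to judge how closely patients stayed at the planned dose per kg would be reading a mixture of dosing and weight change.

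**Working it through.** **No plan figure to reproduce.** The documents give no expected exposure or dose intensity, so the check puts the protocol's AIBW rule through the SAP's formula.

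**Inputs**
- AIBW and IBW formulas and the 10% re-weighing rule: protocol 5.4.3.1.
- Dose 6 mg/kg AIBW: protocol 5.2.2. Next lower level 5 mg/kg: protocol Table 4.
- Exposure formula: SAP 6.1.
- Assumed, not in the documents: height 165 cm, starting weight 75 kg, a 12% loss to 66 kg, nine infusions all at 6 mg/kg, new weight used from the fourth.

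**Step 1: the two AIBWs**
- IBW = 0.9 × 165 − 92 = 56.5 kg
- AIBW at 75 kg = 56.5 + 0.4 × (75 − 56.5) = 63.9 kg
- AIBW at 66 kg = 56.5 + 0.4 × (66 − 56.5) = 60.3 kg

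**Step 2: mg given**
- Infusions 1 to 3: 6 × 63.9 = 383.4 mg each
- Infusions 4 to 9: 6 × 60.3 = 361.8 mg each
- Total = 3 × 383.4 + 6 × 361.8 = 3321 mg; mean per infusion = 3321 / 9 = 369.0 mg

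**Step 3: the SAP formula under each choice of AIBW**

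| AIBW in the denominator | mg/kg/dose |
|---|---|
| Baseline, 63.9 kg | 369.0 / 63.9 = 5.77 |
| Last, 60.3 kg | 369.0 / 60.3 = 6.12 |
| Mean over infusions, (3 × 63.9 + 6 × 60.3) / 9 = 61.5 kg | 369.0 / 61.5 = 6.00 |
| Own AIBW for each infusion, then averaged | 6.00 |

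**Step 4: size per affected infusion (baseline AIBW).** The relative error is the change in AIBW divided by baseline AIBW, or 0.4 × weight change / AIBW.
- 10% change: 0.4 × 7.5 / 63.9 = 4.7%
- 20% change: 0.4 × 15 / 63.9 = 9.4%
- Over assumed heights of 150 to 170 cm and weights of 50 to 110 kg: 3.5% to 6.3% at a 10% change, and 7.1% to 12.6% at 20%
- For scale, one dose level is (6 − 5) / 6 = 16.7%

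**Step 5: does an averaged AIBW settle it?** Only while the dose level is constant. Assume 160 cm and 70 kg (IBW 52, AIBW 59.2), a 10% loss to 63 kg (AIBW 56.4), four infusions at 6 mg/kg before the change and four at 5 mg/kg after it. The true mean is 5.50.
- Total = 4 × 6 × 59.2 + 4 × 5 × 56.4 = 2548.8 mg; mean per infusion = 318.6 mg
- Baseline AIBW: 318.6 / 59.2 = 5.38
- Last AIBW: 318.6 / 56.4 = 5.65
- Averaged AIBW: 318.6 / 57.8 = 5.51

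The averaged AIBW is close. Only the per-infusion calculation is exact by construction.

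**Step 6: effect on the group mean.** In the example of Steps 1 to 3 the patient-level shortfall with baseline AIBW is 6.00 − 5.77 = 0.23 mg/kg. If an assumed 10% of patients were affected in this way and in the same direction, the group mean would move by 0.1 × 0.23 = 0.02 mg/kg; at 30% it would move by 0.07. Gains and losses partly cancel.

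**The case against.** The strongest reply is that the error is not written into the plan. SAP 6.1 says AIBW without saying baseline, and the baseline listing in SAP 4.1.2 does not define the exposure denominator. A programmer could use the dosing AIBW at each infusion and get the right answer. It is true that the SAP gives no instruction to use baseline, and a reader who infers one goes beyond the text. The reply does not clear the formula, however. As written it takes a patient's total mg, divides by the record count and then by one weight, and either obvious choice of that weight fails for a re-weighed patient. An averaged AIBW nearly repairs it, but the SAP does not specify one.

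A second reply is that the effect is small. That stands for the group summary: the documents do not say how many patients will be re-weighed, and excluding fluid-related changes limits the number. For an individual re-weighed patient the error is a noticeable part of a dose level, as Step 4 shows.

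A reader might also infer that a patient held at 6 mg/kg would be counted as dose-reduced. The documents do not support that. No SAP rule derives a reduction from mg/kg/dose. Decreased infusions and TEAEs leading to dose reduction are counted separately, and protocol Table 4 defines reductions as steps from 6 to 5 to 4 mg/kg.

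**Conclusion.** The point holds as a minor flaw in one descriptive exposure statistic. For a re-weighed patient, any one fixed AIBW, baseline or last, misstates the mg/kg per dose. In the assumed example baseline AIBW gives 5.77 instead of 6.00, and the per-infusion error at the 10% threshold is about 4.7%. These sizes rest on assumed heights, weights and timing, and the number of patients affected is unknown. Dose-reduction counts, ORR, alpha and power do not use this statistic and are unchanged.

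A reader might want to extend the point to Grade 2 infusion reactions, because the SAP's definition of dose modification does not mention interrupted infusions. The documents do not make that an error. Protocol Table 7 has such an infusion resumed and completed, so a definition limited to reduction or delay is coherent. The reactions themselves are covered by the TEAE tables, by the hypersensitivity query table by grade in SAP 6.2.2 where the preferred term falls in that query, and potentially by the listing of administration forms in SAP 6.1.

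**What to change.** In SAP 6.1, replace the formula with a per-infusion one: mg given divided by the AIBW in force at that infusion, averaged over the patient's valid administration records. State that this AIBW comes from recorded height and the dosing weight under protocol 5.4.3.1. For a patient whose weight was never reset, the result is identical to the present formula, because the constant AIBW factors out of the average.

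The cost is minor reprogramming, and SAP 1.1 allows changes before final database lock. The condition is that the dosing weight, or the AIBW used, is recorded for each infusion. The case report form is not among the documents, so this needs checking. The Day 1 weights in protocol Table 2 may not be enough by themselves, because a change attributed to fluid does not reset the dosing weight. If the dosing weight is not recorded, the SAP should at least name the AIBW it uses and report how many patients were re-weighed. No dosing rule needs to change.
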